6.3.2.2. Analysis

6.3.2.2.1. Continuous Variable

Summary statistics for OCS dose and change from baseline (percent and absolute) to each scheduled visit will be provided by treatment group.

Analysis of the change from baseline to each scheduled visit will be performed using a mixed effect model for repeated measures (MMRM) including fixed effects for treatment, visit, treatment by visit interaction, age (12 to <18 years and ≥ 18 years), OCS dose at baseline (>10 mg and ≤ 10 mg); baseline OCS dose and duration of OCS use prior to study entry as covariates, and patient as a random effect (see Section 6.4.3.2 for sample SAS[®] code for the MMRM model). Age and OCS dose at baseline will be based on data recorded in the clinical database. An unstructured covariance matrix will be used for the within patient correlation modeling. If the fit of the unstructured (UN) covariance matrix fails to converge, the following covariance structures will be tried in order until convergence is reached: first order autoregressive (AR[1]) and compound symmetry (CS). Based on the MMRM model, the treatment effect, the difference from placebo, and the associated 95% CI will be presented together with the corresponding p-value.

Model results will only be reported if there are at least 15 patients contributing to the analysis in each treatment group; otherwise only descriptive statistics will be displayed. A line graph presenting the LS mean change from baseline over time (at each visit) will be provided for OCS dose by treatment group.

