9.5.6.3. Secondary Efficacy Analysis

All efficacy variables will be summarized by treatment group. For continuous variables, the summary statistics will include n, mean, SD, SE, median, minimum, and maximum. For categorical variables, patient counts and percentages will be provided.

The proportion of patients achieving $\geq 50\%$ reduction in OCS dose at weeks 20 to 24 while maintaining asthma control, proportion of patients achieving dose reduction to ≤ 5 mg daily dose at weeks 20 to 24 while maintaining asthma control, proportion of patients achieving less than 5 mg decrement in OCS dose (ie, the minimal and non-responders) at weeks 20 to 24 while maintaining asthma control, and proportion of patients discontinuing OCS at weeks 20 to 24 will be analyzed using a logistic regression model. The model will include the treatment group and randomization stratification factors as model factors and the OCS baseline dose and duration of historical OCS use (ie, before screening) as covariates.

For the secondary analysis, patients who discontinue the study drug early will be considered as nonresponders and will be categorized in the lowest category of response

Analysis of the mean percentage change from baseline in OCS dose at weeks 20 to 24 will use an analysis of covariance model with treatment group and stratification factors as model factors and the OCS baseline dose and duration of historical OCS use (ie, before screening) as covariates.

The frequency of CAEs will use the negative binomial (NB) regression model. The primary NB model will include the treatment group and randomization stratification factors as model factors and an offset variable. The offset variable will be calculated as the logarithm of follow-up duration minus the summed duration of exacerbations. The ratio of CAE rate between the treatment groups and its 95% confidence interval (CI) will be estimated from the NB model.

Additional covariates or factors may be added to the statistical models. These will be detailed in the statistical analysis plan.

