2.1.4. Treatment Period

Patients continuing to meet eligibility criteria on the day of randomization (day 1, week 0) will be randomly assigned in a 1:1 ratio to receive placebo or reslizumab 110 mg once every 4 weeks

through week 20, followed by an EOT visit at week 24. Patients will begin treatment on day 1 after completing baseline assessments, and they will return to the research facility for outpatient visits every 4 weeks through week 24 (EOT visit) for safety, PK, PD, immunogenicity, and efficacy assessments as applicable.

During the treatment period, the patient will continue his/her usual non-OCS background asthma medication without change; the OCS dose will be tapered per protocol. The treatment period consists of the following:

- **Induction:** The minimally effective dose of OCS will be maintained, unchanged, during the first 4 weeks of the treatment period to allow sufficient time for any potential treatment effect to become established.
- **OCS reduction:** The minimally effective OCS dose will be reduced per protocol at scheduled clinic visits from the beginning of week 5 (ie, end of the induction period) through week 20, as long as all 5 criteria in [Table 2](#) are met and there are no clinical manifestations of adrenal insufficiency. These 5 eligibility criteria assure that the patient's asthma control is not significantly worsened compared to baseline. The last possible dose reduction can occur at week 20. The algorithm for OCS reductions during the treatment period is given in [Table 3](#). If the OCS dose could not be decreased, it should be held constant or may be increased to a previous level, at the investigator's discretion, until dose reduction criteria are met.
- **Maintenance:** OCS dose will be held stable from week 20 through EOT at week 24.

Table 2: Eligibility Criteria for Scheduled Oral Corticosteroid Reductions During the Treatment Period (Must Meet All)

1.	Forced expiratory volume in 1 second (FEV ₁) ≥80% of baseline ^a
2.	AM PEF ≥80% of baseline mean AM PEF on at least 5 of the 7 days preceding the visit
3.	Mean nighttime awakenings due to asthma requiring rescue inhaler over the preceding 7 days ≤150% increase over the baseline period
4.	Reliever bronchodilator inhaler use does not exceed 150% of the baseline inhaler use per 24 hours on more than 2 of the preceding 7 days
5.	No increase in OCS dose since the previous visit ^b

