6.2. Primary Efficacy Variable(s) and Analysis

6.2.1. Variable Definition

The primary efficacy variable for this study is the categorized percent reduction in the daily OCS dose during weeks 20 to 24 as compared with the OCS dose at the end of the optimization phase.

The week 20 to 24 maintenance dose and corresponding values for absolute and percent change (reduction) from baseline will be calculated as follows:

- **Baseline dose** = the prescribed optimized OCS dose following the OCS optimization period ([Table 8](#))
- **Maintenance dose** = mean of all daily OCS doses during the maintenance period extending from Week 20 to Week 24 ([Table 8](#))
- **Absolute reduction** = maintenance dose – baseline dose
- **Percent reduction** = $100 \times (\text{absolute reduction} / \text{baseline dose})$

For both the primary and secondary efficacy analyses, OCS dose will refer to the total daily dose of oral prednisone prescribed for asthma (as per CRF), unless otherwise noted.

The 5 categories for the primary analysis of percent reduction during weeks 20 to 24 are:

- 90% to 100% reduction
- 75% to <90% reduction
- 50% to <75% reduction
- >0% to <50% reduction
- No decrease in OCS, or loss of baseline asthma control during weeks 20 through 24, or discontinuation from study drug

Loss of baseline asthma control will be defined as FEV₁ value of <80% of baseline at the week 24 visit, or clinically significant worsening in ACQ-6 score (increase ≥ 0.5) at the week 24 visit compared with baseline, and/or clinical asthma exacerbation during weeks 20 through 24 (CAE defined in [Section 6.3.3.1](#)).

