6.3.1. Secondary Variables

The secondary efficacy endpoints for this study are as follows:

- Proportion of patients achieving $\geq 50\%$ reduction in OCS dose at weeks 20 to 24 relative to the OCS dose at the date of randomization (DoR)/baseline, while maintaining asthma control

- Proportion of patients achieving dose reduction to ≤ 5 mg daily dose at weeks 20 to 24, while maintaining asthma control
- Percent change from DoR/baseline in OCS dose at weeks 20 to 24
- Proportion of patients achieving less than 5 mg decrement in OCS dose (ie, the minimal and non-responders) at weeks 20 to 24 compared with the OCS dose at DoR/baseline, while maintaining asthma control
- Annualized rate of clinical asthma exacerbations requiring a burst of systemic corticosteroid (injection, or if oral, at least a doubling from the current OCS dose for at least 3 days); an asthma-specific hospital admission; or an asthma-specific emergency department visit during the treatment period (weeks 0 to 24)
- Proportion of patients discontinuing OCS at weeks 20 to 24, while maintaining asthma control

Testing of the secondary variables will be performed using the sequential testing procedure in the order specified above, as described in Section 4.3.

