6.3.2.1. Variable Definition

6.3.2.1.1. Continuous Variable

The post-baseline values for OCS dose and corresponding values for absolute and percent change from baseline will be calculated as follows:

- **Baseline dose** = the prescribed optimized OCS dose following the OCS optimization period (Table 8)
- **Post-baseline dose** = mean of all daily OCS doses during each defined analysis period (Table 8)
- **Absolute reduction** = post-baseline dose – baseline dose
- **Percent reduction** = $100 \times (\text{absolute reduction} / \text{baseline dose})$

Table 8: Definition of Analysis Days for OCS Dose

Analysis period	Start day	Stop day
Baseline Dose	Day of first dose of study drug	N/A
Baseline to Week 4	Day of first dose of study drug + 1 day	Day of W4 Visit
Week 4 to Week 8	Day of W4 Visit + 1 day	Day of W8 Visit
Week 8 to Week 12	Day of W8 Visit + 1 day	Day of W12 Visit
Week 12 to Week 16	Day of W12 Visit + 1 day	Day of W16 Visit
Week 16 to Week 20	Day of W16 Visit + 1 day	Day of W20 Visit
Week 20 to Week 24 (Maintenance Dose)	Day of W20 Visit + 1 day	Day of W24 Visit

DoR=Day of Randomization

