6.4.3.2. Analysis

Summary statistics of actual values and change from baseline to each scheduled visit will be provided by treatment group.

Analysis of the change from baseline to each scheduled visit will be performed using a mixed effect model for repeated measures (MMRM) including fixed effects for treatment, visit, treatment by visit interaction, age group (12 to <18 years and ≥18 years), OCS dose at baseline (>10 mg and ≤10 mg), and sex, height and baseline value as covariates, and patient as a random effect. Age and OCS dose at baseline will be based on data recorded in the clinical database. An unstructured covariance matrix will be used for the within patient correlation modeling. If the fit of the unstructured (UN) covariance matrix fails to converge, the following covariance structures will be tried in order until convergence is reached: first order autoregressive (AR[1]) and compound symmetry (CS). Based on the MMRM model, the treatment effect, the difference from placebo, and the associated 95% CI will be presented together with the corresponding p-value.

The following sample SAS[®] code pertains to the MMRM analysis.

```
proc mixed data=<<>>;
  class patient visit treatment strata1 strata2 sex;
  model change=treatment strata1 strata2 sex height baseline visit treatment*visit
    /ddfm=kr alpha=0.05;
```

```
repeated visit /type=un subject=patient r;  
lsmeans treatment*visit / diff cl;  
ods output lsmeans=<<>>;  
ods output diffs=<<>>;  
run;
```

Model results will only be reported if there are at least 15 patients contributing to the analysis in each treatment group; otherwise only the descriptive statistics will be displayed. A line graph presenting the LS mean change from baseline over time (at each visit) will be provided for pre-bronchodilator FEV₁, FVC, FEF_{25%-75%} by treatment group.

Pre-bronchodilator FEV₁ at Week 24 will additionally be examined for the selected subgroups defined in Section 3.4. The analysis of subgroups will use a MMRM model similar to the one described above. Subgroups will be presented graphically using forest plots.

The proportion of patients achieving an increase of ≥ 100 mL in FEV₁ from baseline to each scheduled visit will be summarized. A stratified (based on randomization strata) Cochran-Mantel-Haenszel (CMH) test will be used to analyze the proportion of patients achieving an increase of ≥ 100 mL in FEV₁ from baseline to Week 24.

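### The MMRM for change in OCS dose shares one covariate slope across all periods, including the fixed-dose weeks 0-4, so with unstructured covariance the weeks 20-24 comparison is in effect unadjusted and loses precision

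*SAP*

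**What the plan says.** The endpoint is "Percent change from DoR/baseline in OCS dose at weeks 20 to 24", third in the fixed sequence of SAP 6.3.1. For its analysis, SAP 6.3.2.2.1 states: "Analysis of the change from baseline to each scheduled visit will be performed using a mixed effect model for repeated measures (MMRM) including fixed effects". The fixed effects listed are treatment, visit, treatment by visit, age group and OCS stratum, followed by "baseline OCS dose and duration of OCS use prior to study entry as covariates, and patient as a random effect". The section refers to sample code in SAP 6.4.3.2, written for lung function, which has the same shape: "model change=treatment strata1 strata2 sex height baseline visit treatment*visit". In both places treatment is the only term that interacts with visit.

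The first post-baseline period in SAP Table 8 starts on "Day of first dose of study drug + 1 day" and ends on the day of the week 4 visit. SAP 2.1.4 says of that interval: "The minimally effective dose of OCS will be maintained, unchanged, during the first 4 weeks of the treatment period". The covariance is unstructured (UN), with AR(1) and then compound symmetry (CS) tried only if UN does not converge. On what counts as dose, SAP 6.2.1 says "OCS dose will refer to the total daily dose of oral prednisone prescribed for asthma (as per CRF), unless otherwise noted". SAP 6.3.2.2.3 treats CAE as a separate indication when it sums steroid burden.

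Protocol 9.5.6.3 planned something different: "Analysis of the mean percentage change from baseline in OCS dose at weeks 20 to 24 will use an analysis of covariance model", with the stratification factors, baseline dose and OCS duration in the model. SAP Table 13 lists only the added covariate in the negative binomial model as a change from the protocol.

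**The concern.** The covariates are there to sharpen the weeks 20-24 comparison. A common slope can do that only if the covariates relate to the outcome in much the same way in every period. Here they cannot: in weeks 0-4 the change is close to zero for nearly everyone, whatever the baseline dose or duration of OCS use. Generalised least squares gives most weight to the period with least variance, and that is the period that carries no information on the slope.

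This runs against the SAP's own intention. In discussing collinearity, SAP 6.2.2 says of the primary model and of the related models in 6.3.2.2 that OCS dose should still do its job as a control variable. At stake is the precision of a gated test. If it misses, three later endpoints lose inferential status: the less-than-5-mg decrement, the CAE rate and OCS discontinuation.

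**Working it through.** **The plan's own figure.** The documents give no figure for this model, only the sample size for the primary endpoint (SAP 2.3). The Whitehead formula is n per arm = 6(z₀.₉₇₅ + z₀.₉₀)² / [(ln OR)²(1 − Σp̄³)]. The placebo proportions are 0.109, 0.079, 0.148, 0.108 and 0.556. An odds ratio of 2.63 gives 0.243, 0.135, 0.193, 0.106 and 0.323 on reslizumab, so Σp̄³ = 0.098. Then n = 6 × 10.51 / (0.935 × 0.902) = 74.7, against 76 planned; power at 76 is 90.5%. The design figure is reproduced.

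**Why the slope collapses.** With complete data and separate intercepts and treatment effects at each period, the common slope is g = Σ wⱼbⱼ. Here bⱼ is the slope in period j, w = S⁻¹1 / (1ᵀS⁻¹1), and S is the residual covariance. If periods were uncorrelated, weights would go as 1/SD². With a simulated SD of 3.4 points in weeks 0-4 and 40.2 in weeks 20-24, the first period would outweigh the last by (40.2/3.4)² ≈ 140 to 1. Correlation between later periods can push the first weight slightly above 1.

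**Simulation, prescribed-dose reading, UN.** Inputs from the documents: 76 per arm and the SAP Table 3 taper. Assumed: the mix of baseline doses, covariate strength, and 2-10% of patients with a small week 0-4 change (2.5 mg above the pre-burst dose).
- Weight on weeks 0-4: 1.01 to 1.05.
- Baseline-dose slope: −0.01 to −0.05 points per mg in the SAP model, against 0.9 to 1.7 when weeks 20-24 has its own slope.
- Correlation of the treatment estimate with the unadjusted difference: at least 0.9998.

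**Size of the loss.** SE of the weeks 20-24 difference, in percentage points. The first three rows come from one simulation in which duration also predicts outcome; the last two from another in which baseline dose does.

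| Assumed R² | Adjusted at weeks 20-24 | SAP model | Unadjusted | SAP / adjusted |
|---|---|---|---|---|
| 8% | 5.44 | 5.57 | 5.57 | 1.02 |
| 16% | 5.23 | 5.61 | 5.61 | 1.07 |
| 31% | 4.76 | 5.60 | 5.61 | 1.18 |
| 7.5% | 6.21 | 6.46 | 6.45 | 1.04 |
| 16% | 5.97 | 6.54 | 6.55 | 1.10 |

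At R² of 3% the loss is about 1-2%. The approximation 1/√(1 − R²) gives 1.5%, 4%, 9% and 20% at 3%, 7.5%, 16% and 31%, the same order. SAP 6.3.2.2.1 does not say whether the modelled change is percent or absolute; for absolute change in mg the inflation was about 6-14%.

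**Power at this step.** Assume category midpoints of 95, 82.5, 62.5, 25 and 0 percent reduction. The design proportions then give means of 28.8 and 49.0, a difference of 20.1 points. Power is Φ(20.1/SE − 1.96). For the five rows, adjusted against SAP model: 95.9% v 95.1%, 97.1% v 94.8%, 98.8% v 94.9%, 90.0% v 87.6% and 92.1% v 86.8%. The loss is about 1 to 5 points.

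**Where the result softens.** Slope as a share of the weeks 20-24 slope:
- AR(1): 55-58%.
- CS: 67-73%.
- UN with burst doses counted: about 10% if 2% of patients have a week 0-4 burst, and 22-40% if 5-20% do.
- No week 0-4 change in any patient: the UN matrix is singular (rank 5 of 6), so the fallback applies.

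**The case against.** The strongest reply is that the effect is conditional and modest, and several parts of that stand.

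A reader might infer that the covariates do nothing whichever model is fitted. The documents do not support that. It needs UN to converge and bursts to be left out of the dose. The wording in SAP 6.2.1 and 6.3.2.2.3 points to bursts being left out, but no sentence excludes them outright.

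A reader might also infer bias. Randomisation keeps the complete-data estimate unbiased, and simulated mean estimates agreed within about 0.3 points. Stratified randomisation already limits imbalance in age group and OCS dose category. Duration of use, and dose within a stratum, are not balanced by design.

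The size is assumed. Nothing in the documents supports 31% in particular, and describing the loss as equivalent to about 28% of patients (1 − (4.76/5.60)²) would present the top of the range as the expectation. Nor is this clearly the step most likely to stop the sequence. On the same design proportions the first secondary compares 33.6% with 57.1%, for about 85% unadjusted power.

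Finally, returning to the protocol ANCOVA is not free. The analysis is on-treatment and uses observed data only, so a single-period ANCOVA drops the earlier visits of patients who discontinue. The simulations had no dropout and cannot weigh that.

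What does not stand is the idea that these limits rescue the first-choice model. None of them restores the intended adjustment.

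**Conclusion.** The concern holds in conditional form. Under UN covariance and the prescribed-dose reading, the weeks 20-24 treatment difference is in effect unadjusted, contrary to the SAP's stated intention. Under the fallback structures, or with bursts counted, the adjustment is weakened. The consequence is an SE wider by about 1-2% at an R² of 3%, rising to about 18% at 31%, and no bias. On the design-based effect of 20.1 points, that costs about 1 to 5 points of power.

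As a separate benchmark, a test with exactly 90% power under proper adjustment would fall to about 88% if the SE were 4% wider and 84% if it were 9.5% wider; the documents state no power for this endpoint.

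The estimates rest on complete data, assumed covariate strengths and an assumed dose mix. The midpoint calculation also sets the lowest category to zero change, although the continuous endpoint does not treat those patients that way. This is a cheap improvement worth making, not a threat to validity.

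**What to change.** In SAP 6.3.2.2.1, add interactions with visit for baseline OCS dose, OCS duration, age group and OCS stratum. With complete data this reproduces the protocol's ANCOVA adjustment at weeks 20-24 while still using earlier visits of patients who stop. It adds 4 × 5 = 20 coefficients over six periods, but only four covariate slopes act at any one visit, as in the ANCOVA, in about 152 patients.

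A lesser alternative is to leave the Baseline-to-Week-4 period out of the MMRM. That removes the dominant weight and the risk of a singular matrix. The remaining five periods would still share one slope, however, and it would lean towards weeks 4-8, where the simulated SD is about 20 points against about 40 at weeks 20-24. It is therefore a partial repair.

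Either way, list the change from ANCOVA to MMRM in SAP Table 13 and settle the wording before unblinding.

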^a Baseline for clinic visit measures (FEV₁) is the DoR value. Baseline for diary measures is the average over the 7 days prior to DoR.

^b If a dose increase results in a return to the previous dose, then it is acceptable to attempt dose decrease again at the investigator's discretion.

AM=morning; DoR=date of randomization; FEV₁=forced expiratory volume in 1 second; PEF=peak expiratory flow; OCS=oral corticosteroid.

Table 3: Oral Corticosteroid Decrements During the Treatment Period

Time Course	Oral OCS Dose (mg/day)								
Optimized OCS dose	40	35	30	25	20	15	10	7.5	5
1 st reduction	30	25	20	15	10	10	7.5	5	2.5
+ 4 weeks	20	15	10	10	7.5	7.5	5	2.5	0
+ 4 weeks	10	10	5	5	5	5	2.5	0	
+ 4 weeks	5	5	2.5	2.5	2.5	2.5	0		
+ 4 weeks	2.5	2.5	0	0	0	0			

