2.1.4.1. Handling of Asthma Exacerbations During the Treatment Period

Patients should be treated with an OCS burst: 40 to 60 mg (or at least double the current dose) of OCS tapered over a 7- to 10-day period to a new maintenance dose of 2.5 mg above the pre-burst dose. It is understood that im or iv corticosteroid may also be administered as part of the treatment of the asthma exacerbation. If a second OCS burst (doubling of current dose) is required, the patient should be maintained on a fixed OCS dose without any tapering attempts for the remainder of the double-blind treatment phase and the follow-up period.

Patients who complete all scheduled visits will have final procedures and assessments performed at the EOT visit (visit 19). Patients who withdraw from the study before completing the 24-week treatment period will have visit 19 (week 24 ± 7 days or early termination) procedures and assessments performed at their final visit. Patients will return for a follow-up evaluation 8 weeks (±7 days) after the EOT visit in this study for assessment of pre-bronchodilator spirometry, ACQ-6 score, PK samples, adverse events, blood eosinophils, CAEs and related health care utilizations, and blood for ADA.

The assessments and procedures performed during each study visit are detailed in [Table 4](#). If a patient elects to withdraw (or is discontinued from treatment by the investigator), every attempt will be made to continue the assessments subsequent to his/her withdrawal from the study.

Table 4: Study Procedures and Assessments

Procedures and assessments	Pretreatment		V12 Start run-in	Double-blind treatment period (visit/week)							Follow-up	Late follow-up
	V1	V2-V11		V13 ^a	V14 ^a	V15 ^a	V16 ^a	V17 ^a	V18 ^a	V19 ^a	V20	V21
	Start of screening period	Standardize and optimize maintenance OCS ^{abc}										
	Week -14 ^d	Between weeks -12 and -3		W -2	DoR	W4±7d	W8±7d	W12±7d	W16±7d	W20±7d	W24±7d/ EOT/ early termination	W32/EOT + 8w ±7d
Informed assent/consent	X											
Medical history	X											
Medication history	X											
Inclusion and/or exclusion criteria	X	X ^e	X	X								
Randomization criteria				X								
Reversibility testing ^f	X											
Pregnancy testing ^g	X			X	X	X	X	X	X	X	X	
Blood for HIV, hepatitis B, and hepatitis C	X											
CBC with differential ^h	X	X	X	X	X	X	X	X	X	X	X	
Serum chemistry tests ⁱ	X			X	X ^j	X ^j	X	X ^j	X ^j	X		
Urinalysis	X											
Full physical examination ^k	X											

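### If the unstructured model for percent change in OCS dose fails, the AR(1)/CS fallback assumes equal variances that the taper design rules out, so the weeks 20-24 standard error would be too small

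*SAP*

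**What the plan says.** SAP 6.3.1 lists percent change from baseline in OCS dose at weeks 20 to 24 as the third secondary endpoint. Section 4.3 tests in fixed sequence at two-sided 0.05, so this is the fourth test. Section 6.3.2.2.1 fits an MMRM over the six post-baseline periods of Table 8, with an unstructured covariance matrix. If that does not converge, "the following covariance structures will be tried in order until convergence is reached: first order autoregressive (AR[1]) and compound symmetry (CS". The sample code it points to, in Section 6.4.3.2, has "repeated visit /type=un subject=patient r" with Kenward-Roger degrees of freedom and no empirical standard error.

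The design shapes the spread of this variable. Section 2.1.4 says of induction: "The minimally effective dose of OCS will be maintained, unchanged, during the first 4 weeks of the treatment period". Reductions then follow Table 3 ("Oral Corticosteroid Decrements During the Treatment Period") from week 4 onward, and "The last possible dose reduction can occur at week 20". After an exacerbation, Section 2.1.4.1 provides for "a new maintenance dose of 2.5 mg above the pre-burst dose". Table 8 closes the Baseline to Week 4 period on the "Day of W4 Visit". Section 6.3.2.2.3 adds a Wilcoxon rank-sum test as a sensitivity analysis.

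**The concern.** AR(1) and CS differ in correlation pattern but share one feature: a single variance for every period. Here the variances cannot be equal. Percent change is near zero for almost everyone in the first period. Patients then separate as some taper fully and others not at all. A pooled variance averages the quiet early periods with the late ones, so it understates the period being tested.

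One data pattern that can make the unstructured matrix singular, a first period with no variation, is also the pattern that the equal-variance structures describe worst. At stake are the reported treatment difference with its 95% interval, and a p-value that opens the last three secondary tests, including the exacerbation rate.

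**Working it through.** **1. The plan's own figure.** The documents give no SD, SE or power for this endpoint. The only sizing figure is for the primary: 76 per group, 90% power, odds ratio 2.63. The ordinal formula is N = 12(z₀.₉₇₅ + z₀.₉₀)² / {(ln OR)²[1 − Σp̄³]}. The stated placebo distribution gives averaged proportions 0.176, 0.107, 0.170, 0.107, 0.439, so 1 − Σp̄³ = 0.902. Then N = 12 × 10.51 / (0.935 × 0.902) ≈ 149.4, or 75 per arm, and power at 76 per arm is 90.5%. It reproduces, and 76 per arm is used below.

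**2. Hand check for CS.** Assumed SDs by period (percentage points), from a Table 3 taper with an assumed starting-dose mix: 0, 20, 31, 37, 40, 41. With complete data and no covariates, CS fits the mean variance:
- pooled SD = √[(0 + 400 + 961 + 1369 + 1600 + 1681)/6] = √(6011/6) = 31.7
- SE under CS = 31.7 × √(2/76) = 5.13; SE from the weeks 20-24 variance = 41 × √(2/76) = 6.65
- ratio = 0.77; null error = 2[1 − Φ(1.96 × 0.77)] ≈ 0.13; coverage ≈ 0.87

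**3. Simulation with dropout and covariates, fallback forced.** REML fits, 76 per arm, two taper models, 9-13% missing at weeks 20-24.

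| | AR(1) | CS |
|---|---|---|
| SE / true SE | 0.73-0.78 | 0.76-0.81 |
| Null error | 13.9-16.1% | 13.3-14.0% |
| 95% CI coverage, true difference 18-22 points | 86-88% | 87-89% |

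An unstructured fit on five periods gave 95-96% coverage in the same settings. Adding a patient intercept to AR(1) left the null error at 13.9%.

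**4. Dependence on the assumed spread.** Shortfall in the SE:
- Table 3 tapers, large sample: 25-29% (AR(1)), 21-30% (CS)
- burst doses counted in the daily dose: 22% at 8% of patients per period, 16-20% at 15%
- early plateau (5, 30, 38, 40, 40, 40): 14-19%
- spread falling late (5, 25, 38, 42, 40, 36): 7-15%
- linear growth (2 to 50): 34-39%
- equal SDs: 0%

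**5. How often the fallback would be reached.** Two patterns make the unstructured matrix singular.
- *No analysed patient has a first-period change.* If a share s changes, the chance is (1 − s)¹⁵²: 47%, 22%, 4.6%, 1.0% and 0.04% for s = 0.5%, 1%, 2%, 3% and 5%. A post-burst increment can supply a change. So can a reduced dose recorded on the week 4 visit day, because Table 8 includes that day.
- *No analysed patient's dose differs between weeks 16-20 and 20-24.* In Table 3, starts of 5, 7.5 and 10 mg that taper on schedule have no step left at week 20. This occurred in 12.6% of null trials in a strict taper model (1.5% of patients changing at week 20), 0.7% of trials with an effect (3.5% changing), and none in a looser model.

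If visit-day recording is the only source of first-period change, and 1%, 2%, 5% or 10% of patients record that way, the rule as written has ungated null error of 8.7%, 7.2%, 5.4% and 5.2% in the first taper model. In the second, the unstructured fit also failed in 7-15% of trials despite a first-period change. These fits were not made in PROC MIXED, so when that procedure would report non-convergence is unknown.

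**6. Gate.** With every null true and the fallback forced, this endpoint was rejected after the primary and first two secondaries in about 1.1% of trials.

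**The case against.** The strongest reply is that this contingency may never arise. A reader might infer from the fixed induction dose that the unstructured fit is bound to fail. The documents do not support that: one patient with any first-period change removes the first route. Post-burst increments, investigator increases to a previous level and dose changes for adrenal insufficiency can defeat either route. If 1% of patients change after a burst (22% chance of none) and, independently, 2% record the new dose on the visit day (10-25%), the chance of no mover is only about 2-6%. This stands, and it is why the point is minor.

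Second, the gate. The three earlier tests use the same weeks 20-24 dose, so a true null here alongside real effects there is hard to construct. This also stands for family-wise error. It does not help the 95% interval, which SAP 6.3.2.2.1 says will be presented and which is too narrow with or without an effect.

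Third, the Wilcoxon test needs no covariance structure. True, but as a sensitivity analysis it cannot replace the gatekeeping p-value or correct the interval.

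Fourth, a reader might see an undisclosed change of method, because protocol 9.5.6.3 planned ANCOVA and SAP Table 13 has no row for the switch. The SAP introduction says that the SAP prevails and that differences will be explained in the CSR, so this is clerical. The same goes for "and patient as a random effect" in the model text beside code with only a REPEATED statement, and for text that says change where the endpoint is percent change.

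**Conclusion.** The fallback is not valid for this variable when it is used. The direction follows from the design; the size rests on assumptions. Under assumed Table 3 tapers the weeks 20-24 SE is roughly 20-30% too small, with null error of about 13-17% in central cases and coverage of about 86-89%. Over other assumed unequal-variance paths the shortfall is 7-39%.

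Two stronger readings should be resisted. A reader might infer a fixed shortfall of one quarter; without SDs by period, that is only a central value. A reader might also take 13-17% as the trial's type I error. That figure applies only when the fallback is used and before the gate; family-wise, the effect is small. What remains is a too-narrow interval and an unreliable p-value in front of the last three secondaries, in a situation of unknown and possibly low frequency.

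**What to change.** Keep the unstructured MMRM as the lead analysis, on all six periods. Replace AR(1) and CS with heterogeneous-variance structures (for example TOEPH, ARH(1), CSH) using empirical (sandwich) standard errors, and state the degrees of freedom that go with them. In the fallback only, leave Baseline to Week 4 out of the model and keep its descriptive summary.

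On five periods with empirical SEs, simulated null error was 4.8-4.9% (ARH(1)), 4.1-5.1% (CSH) and 4.8-5.1% (TOEPH), with 95-96% coverage. The empirical SE is needed: without it ARH(1) gave 6.1-6.8% and TOEPH 6.9-11.9%.

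The cost is SAP wording. When the fallback is used, the interval is about one third wider than the AR(1) interval (1/0.75 = 1.33), which is the width the data support. Patients with only first-period data then leave the model; their change is zero or near zero by design. As housekeeping, the same amendment can add the Table 13 row, name percent change as the modelled variable and settle the random-effect wording.
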